that patient. These envelopes are placed in the custody of the Pharmacy Service for the duration of the study. The blind (or treatment assignment) will only be broken if knowledge of the specific drug is essential to the medical management of the patient (See DTHP Section 11 for further information on emergency unblinding of a participant during the study), or at the completion of the study and transfer of care to primary providers (See Section XIV).

The emergency drug code envelope and its contents must be returned to the CSPCRPCC within 72 hours of the code break. Upon receipt of the code envelope, the CSPCRPCC will immediately inform the study biostatistician via telephone or email and send the envelope, which will be filed with the study documents at the MAVERIC CSPCC. When the study has been completed (or terminated early) the unopened envelopes must be returned to the CSPCRPCC. The CSPCRPCC will verify that the envelopes were or were not intact and notify the study biostatistician of their status.

Primary Data Analysis Plan

The primary analysis will be an intention-to-treat survival analysis of all subjects who were randomized and received at least one dose of study medication. The primary hypothesis to be tested is that lithium augmentation of enhanced usual care is superior to enhanced usual care plus placebo for the prevention of repeated episodes of suicidal self-directed violence over time. We posit a one-year repeat rate of 15% in the placebo group and a 37% reduction of events in the intervention group.

The null hypothesis is that the two treatment groups do not differ in their hazard rates. The alternative hypothesis is that the group on lithium augmentation has a lower hazard rate than the placebo augmentation group.

The primary hypothesis can be stated as follows.

Under the null hypothesis: The 1-year event rate will be 15%.

Under the alternative hypothesis for patients treated with lithium: The 1-year event rate will be 9.45%.

The reductions attributed to treatment may be viewed in several ways. The absolute reduction from 15% to 9.45% is 5.55%, the relative reduction is $(15 - 9.45)/15 = 37\%$, and the hazard ratio (treatment hazard rate/control hazard rate) of 0.61 is approximately midway between the simple odds ratio, $[9.45(100-15)] / [15(100-9.45)] = 0.59$ and the risk ratio $9.45/15 = 0.63$.

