On the basis of studies that examined associations between suicide rates and lithium concentrations in drinking water, it has been suggested that lithium may have a preventive effect even at very low plasma levels (Helbich et al., 2012; Kabacs et al., 2011; Kapusta et al., 2011; Ohgami et al., 2009; Schrauzer & Shrestha, 1990). Based on these reports and absence of data

for what constitutes a lower limit for effective plasma levels, dose (and plasma-level) reductions will be allowed for patients who are unable to tolerate 0.6-0.8 mEq/L. The lowest allowable dose of lithium for continued treatment will be 300 mg/day. All patients able to tolerate that dose will be maintained at the highest tolerable plasma level not to exceed 0.6-0.8 mEq/L.

Blinding

This is a double blind placebo-controlled study in which the participant, treating clinicians, and all study personnel, including the Central Psychiatrist/Safety Officer, are blinded to treatment assignment.

All investigators and Outcomes Adjudication Committee members will only see blinded interim reports. Members of the DMC will receive unblinded reports in that they will view study results by treatment group (e.g. A versus B) and these designations will be randomly assigned within a report. The placebo will be produced by the CSPCRPCC and be nearly identical in appearance to the active agent and have similar taste and odor.

Breaking the blind, to the patient's mental health provider, at the end of a participant's time in the study should not compromise the blind for the personnel at the study site nor influence outcome assessments of participants remaining in the study. All ratings and assessments will be completed before the blind is broken. To ensure that the breaking the blind on those who complete the study does not reveal information about the assignment of the last subjects, block randomization is within multiple strata and an extra treatment assignment will be inserted to each stratum of four to disrupt the blocks and mask block sizes, as described in Section VII.

Titrating study medication

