- 1) Calculate a plasma level for the current dose using the method of Abou-Auda (2008).

- 2) Adjust the plasma upwards if there are reports of side effects, and downward, if there are reports of non-adherence; these adjustments are intended to ensure that the simulated plasma levels appear plausible and realistic in light of the patient's clinical status.
- 3) Multiply the adjusted value by a random factor. This is necessary to ensure that there is a realistic degree of week to week variability for simulated plasma levels and that the reported values cannot signal the Research Team at the study site about whether the plasma levels are real or simulated.

During the course of the study, the study biostatistician will periodically compare the distributions of real and simulated plasmas levels to ensure that there are no significant differences. Should there be trends suggesting they are diverging, the biostatistician will work with the MAVERIC data coordinating center to revise the parameters for calculating simulated measures.

All participants will have flags in their VA electronic medical records in accordance with local policy. This study falls under the 1200.05 2012 version, however, we recommend that the flags state that the participants are enrolled in a research study and any medication changes or drug level testing be done only after consulting the Site Physician. The amount of information provided within the flags may vary by site according to local policies and procedures.

The processes for dispensing medication from a VA pharmacy or by mail will be developed for each patient, depending upon whether patients are inpatients (at the start of the study) or outpatients, and whether or not they have convenient access to a VA facility. Medications will be dispensed in blister cards containing medication for two weeks. Some participants may be dispensed one week of medication at a time if the investigator determines this is more appropriate for the safety of the participant. Participants will be asked to return unused blister cards at the next study visit to perform tablet counts to assess adherence.

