If a medical center is placed on probation, the Study Chair will confer with the site personnel and may visit the site, if necessary, to help improve the rate of recruitment. Once a site is placed on probation, failure to meet the requirements specified by the end of the probation period will result in a recommendation for termination. Additionally, sites that fail to meet two or more of

the above performance measures, and sites that habitually under-perform by any of these measures, will be at risk of termination.

To plan for the possible termination of a site(s) and the addition of a new site(s), back-up sites with IRB approval will be identified prior to study initiation to minimize the delay in adding a new site. The Executive Committee will take actions leading to discontinuation of a site only with the concurrence of the CSPCC Director. If a site is terminated from the trial, resources will be reallocated to other medical centers or used to start up a back-up site.

III. Premature Termination of the Study

The Director, CSP, can terminate a cooperative study before completion. The DMC makes recommendations as to whether the study should continue or be terminated. The decision to terminate a study prematurely is a complex one involving many factors. The DMC may consider the following circumstances as grounds for early termination:

1. If patient accrual falls far below that which is predicted (e.g., 75% of expected accrual), it will be necessary to reassess the study design and the potential value of its continuation.
2. If patient accrual far exceeds the predicted, this study could be completed at an earlier date.
3. If serious adverse events or mortality are noted to be excessive in either treatment group.
4. If interim analyses indicate a trend in the data which is unlikely to change prior to study completion.
5. If, during interim analyses on the primary end point, the significance level crosses the efficacy boundary established by the DMC.

Termination by recommendation of the DMC will be carried out as outlined in CSP guidelines.

XVIII. GOOD CLINICAL PRACTICES AND SITE REVIEW PROGRAM

Role of GCP

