The Executive Committee is responsible for the operations of the study, including protocol amendments, and overall management of the study. It will be headed by the Study Chair and Study Director and consist of the study biostatistician, study project manager, clinical research pharmacist, CSP Center Director, selected participating investigators, and outside consultants as needed. This committee will meet regularly to review blinded data (not broken down by treatment group), decide upon changes in the study, determine the fate of hospitals whose performance is substandard, initiate any subprotocols, and discuss publication of the study results. This Committee must grant permission before any study data may be used for presentation or publication.

The Data Monitoring Committee (DMC) will review the progress of the study and will monitor patient intake, outcomes, adverse events, and other issues related to patient safety, including review of study participants with lithium levels of ≥ 1.3 to determine if there is an association with concomitant hypertensive medications and whether the participants' age or eGFR may play a role. Interim, independent, and unbiased reviews of the study's ongoing progress will be provided. The DMC will consist of experts in the study's subject matter field(s),

clinical trials, biostatistics, and ethics. These individuals will not be participants in the trial and will not have participated in the planning of the protocol. The DMC will consider safety or other circumstances as grounds for early termination, including either compelling internal or external evidence of treatment differences or the unfeasibility of addressing the study hypothesis (e.g., poor patient intake, poor adherence to the protocol).

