At each of its meetings during the study period, the DMC will review the randomization rates and assess the difference between the actual and the projected rates, as well as the impact of these assessments on overall trial size. If the study enrollment is inadequate, the reasons for exclusion may be scrutinized and actions may be suggested. An assessment of whether the trial should be continued will be made followed by recommendations, as appropriate. All serious adverse events will be reported regularly to the DMC for review. Unexpected, related serious adverse events will be reported to the DMC as soon as they become known based upon the consensus of the Study Chair, the study biostatistician, the Study Director, and the study pharmacist. The study biostatistician will provide the appropriate data to the DMC at specified intervals for this purpose. Conditional power estimates may be provided to the DMC to assist them in making their decisions and recommendations at their request. To help them make their assessment, the Study Chair and study biostatistician will furnish the Data Monitoring Committee with appropriate monitoring data before each meeting. The DMC makes recommendations after each meeting to the Director of the Clinical Science Research and Development (CSRD) Service about whether the study should continue or be stopped.

The VA Central IRB will be the IRB of record for all VA sites. They will monitor the study's serious adverse events on a continual basis. They will conduct annual reviews of the study. In addition, some study materials (such as subject correspondence and protocol changes) will have to be reviewed by the VA CIRB, and approved prior to implementation.

The **CSPCC Human Rights Committee (HRC)** is composed primarily of lay people and is responsible for ensuring that patients' rights and safety are upheld prior to study initiation and during the conduct of the study. The committee reviews all new protocols, periodically makes site visits to participating centers to monitor firsthand the progress of the study, and may be asked to review any ethical and human rights issues that arise during the conduct of the study.

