10.1. Interim Analysis

We will conduct one interim analysis after half of the participants have completed their 12 month follow up. This analysis is projected to take place approximately 2.5 years after initiation of enrollment (assuming it will take 1.5 years to enroll half the sample and allow 12 months of follow-up). After adjusting for attrition, a sample of 746 evaluable subjects, (373 in each group), is expected to be included in the analysis.

Projecting the same event rate in this sub-sample we expect to observe a 15% or 112 events (56 events in each group) under the interim null hypothesis that event rates are equal in the treatment groups. Under the interim alternative hypothesis, the absolute reduction from 15% to 5.3% is $(15-5.3) = 9.7\%$, the relative reduction is $(15-5.3)/15 = 65\%$, and the hazard ratio (treatment hazard rate/control hazard rate) is 0.34. The interim log-rank test is two-sided, and the interim null hypothesis will be rejected if the hazard ratio exceeds $1/0.34 = 2.94$ or falls below 0.34. Using the O'Brien-Fleming procedure, (Turnbull & Jennison, 2000), this analysis will have a Type I error of 0.2%.

We will confer with the Data Monitoring Committee members and the program leadership for potential stopping guidelines based on results from interim efficacy analysis.

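### The study biostatistician role combines arm-revealing data with an Executive Committee seat and no written firewall, and the interim stopping text leaves room for discretion once results are seen

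*SAP*

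**What the plan says.** **Roles.** The Protocol gives one role title the following duties.

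- Section XIII, Titrating study medication: "the study biostatistician will periodically compare the distributions of real and simulated plasmas levels to ensure that there are no significant differences". Section VIII.G makes clear that simulated levels exist only for placebo participants.
- Section VII, Randomization Plan: after an emergency code break, "the CSPCRPCC will immediately inform the study biostatistician via telephone or email". The opened envelope, which holds the assignment, then goes to the coordinating center.
- Section XIX.B, on the DMC: the study biostatistician provides its data at intervals, and "the Study Chair and study biostatistician will furnish the Data Monitoring Committee with appropriate monitoring data before each meeting".
- Section XIX.B, on the Executive Committee: "It will be headed by the Study Chair and Study Director and consist of the study biostatistician", among others. The committee is to look at data pooled over arms and decide on changes to the study.

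Against this, Section XIII, Blinding, says that "all study personnel, including the Central Psychiatrist/Safety Officer, are blinded to treatment assignment".

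**Stopping.** SAP section 10 sets an O'Brien-Fleming rule with one interim test at p=0.002 and a final test at p=0.048. SAP 10.1 also rejects at the interim if the hazard ratio is below 0.34 or above 2.94. It then adds: "We will confer with the Data Monitoring Committee members and the program leadership for potential stopping guidelines based on results from interim efficacy analysis". Protocol Section VII has a sentence to the same effect. Protocol Section XVII lists, as a ground for early termination, that "the significance level crosses the efficacy boundary established by the DMC".

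**The concern.** Two things looked wrong. First, a role that must know the arms to do its work sits on a committee whose protection is that it does not know them. Restricting what is tabled at that committee does not restrict what a member already knows. Decisions on centers, eligibility or the length of recruitment could then be questioned later, even if nobody acted improperly.

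Second, the efficacy boundary has more than one apparent owner (the SAP, the DMC, and a discussion that includes program leadership) and two numerical forms. If these disagree when interim results arrive, someone has to choose between them with the results in hand. A pre-specified boundary exists to prevent exactly that.

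**Working it through.** **The plan's own figures.** Inputs from SAP section 10 and Table 2: 745 evaluable per arm, one-year rates of 15% and 9.45%, final level 0.048.

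- Events: 745 × (0.15 + 0.0945) = 182.2, against 182 stated.
- Hazard ratio: ln(1 − 0.0945) / ln(1 − 0.15) = 0.611, against 0.61 stated.
- Power with 182 events by Freedman's formula: Φ(√182 × 0.39/1.61 − z), with z the two-sided 0.048 critical value, gives 90.2%, against 90% stated.

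**Overall type I error under the written levels.** Two-look bivariate normal with correlation √t and two-sided levels 0.002 then 0.048.

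- At t = 0.50 (373 × 0.2445 = 91 expected interim events under the design rates; 91/182): 4.86%.
- At t = 112/182 = 0.615 (SAP 10.1's 112 null events): 4.83%.

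If the written levels bind, error is controlled below 5%.

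**Do the two interim rules agree?** With d events and equal allocation, z = −ln(HR) × √d / 2. The hazard ratio that just reaches p=0.002 is exp(−2 × 3.09/√d).

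| Interim events | Basis | HR at p=0.002 | z at HR 0.34 | two-sided p at HR 0.34 |
|---|---|---|---|---|
| 112 | 746 × 0.15 | 0.56 | 5.7 | about 1 × 10⁻⁸ |
| 91 | 373 × (0.15 + 0.0945) | 0.52 | 5.1 | about 3 × 10⁻⁷ |
| 76 | 373 × (0.15 + 0.053) | 0.49 | 4.7 | about 3 × 10⁻⁶ |

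They do not agree at any of these event counts. The 0.34 is the hazard ratio implied by the interim alternative, ln(1 − 0.053)/ln(1 − 0.15) = 0.335, and has been written as if it were a critical value.

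The consequence at a true hazard ratio of 0.61 with 91 events:

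- Probability of p<0.002: Φ(−ln(0.61) × √91/2 − 3.09) = about 23%.
- Probability of an estimate below 0.34: Φ((ln 0.34 − ln 0.61) × √91/2) = about 0.3%.

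An observed hazard ratio of 0.45 would stop the trial under one rule and not under the other.

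**Roles side by side.** Comparing real with simulated levels requires knowing which participants are on placebo, so whoever does it is unblinded. The blinding statement in Section XIII and the level check in the same section cannot both be true. The Executive Committee provision in Section XIX controls the reports shown, and no text separates its biostatistician member from the one who does the level check.

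**The case against.** The other side has several good points.

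- **A stopping rule is written.** SAP section 10 gives both levels, and SAP 4.3 repeats the 4.8%. The sentence in SAP 10.1 can mean guidelines that act on interim results, not guidelines chosen after them, and it names the DMC first. Program leadership also has a legitimate part: the Director can terminate the study, and the DMC reports to the research service's Director. This stands, so a reader who infers that the boundary is left open, or is settled outside the DMC, goes further than the text. What remains is that the sentence allows both readings and does not say who sees results.
- **Type I error.** A reader might infer inflation to 5.9% or 8.2%. Those values arise at t = 0.50 only if the interim threshold became 0.02 or 0.05 with the final test kept at 0.048. No document proposes either threshold.
- **One person?** The Protocol title page lists biostatisticians in the plural, and Section XVI lists a primary and a secondary post. Section XIX says further delineation of responsibilities will be documented elsewhere. The documents therefore show one role title, not one individual. That makes the fix easy, but the split is not written.
- **Allocation is not results.** In SAP 8.3 the outcome tables are open-session only, and tables by arm are confined to safety. This stands in part. The by-arm tables include serious adverse events and deaths, and SAP 4.2 says potential endpoints are found mostly through serious adverse event reports or the Columbia form.
- **The Study Chair.** A reader might infer that the Chair handles arm-level data. No passage says so: the Chair is defined as blinded, and investigators see only blinded interim reports.
- **Scope of changes.** A reader might infer that endpoints could be altered. Section XVII names centers, minor eligibility changes and the recruitment period, all needing DMC and Director approval. It does not name endpoints.

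**Conclusion.** The role conflict is on the face of the Protocol: a role with arm-revealing information belongs to a committee that is meant to work blinded, no firewall is described, and the blinding statement is contradicted by the level check. It has no numerical size, and nothing shows that the Executive Committee would receive results by arm.

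The stopping text holds in a narrower form. The written levels control overall error at about 4.9%. The weakness is ambiguity: three places bear on who owns the boundary, and the hazard-ratio limit of 0.34 is far stricter than p=0.002 (about 0.56 at 112 events, 0.49 to 0.52 at 76 to 91 events). These figures rest on the normal approximation to the log-rank test, equal allocation and the SAP's projected interim sample. That unblinded results will in fact steer the trial is a stronger reading that the documents do not support. Sample size and power are unaffected.

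**What to change.** - Assign the real-versus-simulated comparison, code-break notices and closed DMC reports to one named unblinded biostatistician, using one of the two posts listed in Protocol Section XVI, with no Executive Committee seat.
- Correct the blinding statement in Protocol Section XIII so that it names the unblinded roles.
- State in Section XIX that the Study Chair contributes only open-session material.
- Replace the program-leadership sentence in SAP 10.1 and Protocol Section VII. The new text should say that the p=0.002 log-rank boundary is fixed before any unblinded look, that only the DMC and the unblinded biostatistician see interim results by arm, and that the DMC forwards a recommendation without arm data.
- Align the termination ground in Section XVII with that boundary.
- Delete the 0.34 and 2.94 limits, or recompute them from p=0.002 at the interim event count. Pointing to SAP 10.1 as it stands would keep both rules.

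The cost is wording plus a transfer of some work between two existing posts. The small downside is that the biostatistician on the Executive Committee stays blinded until database lock.

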10.2. Futility Analysis

As a part of the interim futility analysis we will estimate the conditional probability (CP) of observing a significant final result based on assumptions about the distribution of future event rates. Assumptions for additional data to be collected in the second half of the study are:

- (1) “no-change” scenario where future event rates will occur at the same rate as currently observed rates,
- (2) “expected” scenario where future event rates occur at the rates expected at the beginning of the trial (i.e., as proposed in the protocol),
- (3) “extreme” scenario where future event rates occur at the currently observed overall event rate, but all new events occur in the placebo group so as to set the best scenario for achieving a significant difference.

For conditional probability estimation, we will use the estimation method developed by Proschan, Lan, and Wittes, 2006 and further described by Jitlal et. al, 2012, where

CP at a specific time = $1 - \Phi[(Z\alpha/2 - E[B(1)|B(t)])/\sqrt{1-t}]$,

$E[B(1)|B(t)]$ is the expected value of $B(t)$ at the end of the trial (when $t=1$), given the data observed until point t .

The information fraction, t , is the number of observed events so far, expressed as a proportion of the planned number of events.

11. Final Statistical Report

The final statistical report for CSP590 will be the submitted and accepted primary manuscript which includes results from the primary ITT analysis as outlined in section 4 and any additional analyses to be conducted based on the journal's peer review process. At minimum, the final statistical report will include the CONSORT diagram (section 8.3.1), descriptive characteristics of the ITT cohort (section 8.3.2), medical and psychiatric history of the cohort (section 9), and the primary analysis results (section 4.3).

12. References

- MacKinnon, D. P.; Lockwood, C. M. Hoffman, J. M., West S. G., Sheets V. A Comparison of Methods to Test Mediation and Other Intervening Variable Effects. *Psychological Methods* 7: 83–104, 2002
